13.3. Appendix 3: Study Phases

13.3.1. Study Phases

Participants are considered to have entered the Extension phase if they have a Month 14 visit. They are considered to enter the LTFU period if they have a post-treatment, non-bridging ART start date or LTFU visit entered in the CRF, including LTFU withdrawal.

Participants are considered to have completed the Intervention Phase upon successful completion of the Month 12 visit without discontinuing from study treatment. Extension Phase completion is defined as successful transition to commercial product whenever it becomes available by attending a Safety Follow-up visit and not discontinuing treatment.

Table 6 Participant Phase Entry and Conclusion Windows

Phase	Qualifying Entry Timepoint	Qualifying Conclusion Timepoint
Intervention Phase	First CAB + RPV dose date	Month 14 visit date; or Safety Follow-up visit date (if transitioned to commercial product); or LTFU ART start date (if discontinued from treatment after receiving at least one dose of CAB/RPV LA)
Extension Phase	Month 14 visit date	Safety Follow-up visit date (if transitioned to commercial product); or LTFU ART start date (if discontinued from treatment after receiving at least one dose of CAB/RPV LA)
LTFU Phase	LTFU ART start date or LTFU Visit date existence	LTFU Month 12 visit date

AEs will be assigned to study phases as defined in Table 7. Laboratory data (efficacy, safety, and virology), HIV associated Conditions, health outcomes assessments, and vital signs will be assigned to study phases as defined in Table 8.

Assessments/events are assigned to study phases sequentially, starting from the top of each table.

Table 7 Study Phases for AEs

Study Phase	Definition
Screen	Date < Intervention Phase Treatment Start Date
Intervention Phase	
For subjects continuing into the Extension Phase: Intervention Phase Treatment Start Date ≤ Date < Date of Nominal Month 14 Visit
 
For subjects not continuing into the Extension Phase: Intervention Phase Treatment Start Date ≤ Date < LTFU ART Start Date^[a]

Study Phase	Definition
	
For subjects transitioning to commercial product without discontinuing or entering Extension: Intervention Phase Treatment Start Date ≤ Date ≤ Safety Follow-up visit date
 
For AEs leading to treatment withdrawal with start date equal to the LTFU ART Start Date, Intervention Phase instead of Long-term Follow-up Phase will be assigned.

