Extension Phase	
For subjects transitioning to commercial product: Date of Nominal Month 14 Injection ≤ Date ≤ Safety Follow-up visit date
 
For subjects not transitioning to commercial product: Date of Nominal Month 14 Injection ≤ Date < LTFU ART Start Date ^[a]
 
For AEs leading to treatment withdrawal with start date equal to the LTFU ART Start Date, Extension Phase instead of Long-Term Follow-up Phase will be assigned.

Long Term Follow-Up	
For subjects who receive at least one CAB/RPV injection and permanently discontinue study treatment: AE Start Date ≥ LTFU ART Start Date

AEs with completely missing start date:
 
 • If AE end date is ≤ Intervention Phase Treatment Start Date, then assign to Screening Phase; • Else if AE end date is completely missing or Intervention Phase Treatment Start Date < AE end date ≤ Date of Nominal Month 14 Injection, then assign to Intervention Phase; • Else if AE end date > Date of Nominal Month 14 Injection, then assign to Extension Phase. 	

- Date=AE Start Date
- [a] If participants have missing LTFU ART start date, only the lower bound will be considered in the derivation.

Table 8 Study Phases for Laboratory, Vital Signs, HIV-1 Associated Conditions, and Protocol Deviation Data

Study Phase	Definition
Screen	Date ≤ Study Treatment Start Date
Intervention Phase	
For subjects continuing into the Extension Phase: Intervention Phase Treatment Start Date < Date < Date of Nominal Month 14 Visit
 
For subjects not continuing into the Extension Phase: Intervention Phase Treatment Start Date < Date ≤ LTFU ART Start Date ^[a]
 
For subjects transitioning to commercial product without discontinuing or entering Extension: Intervention Phase Treatment Start Date < Date ≤ Safety Follow-up visit date

Extension Phase	
For subjects continuing into Extension Phase: Date of Nominal Month 14 Visit ≤ Date ≤ LTFU ART Start Date ^[a] or Safety Follow-up visit date

Long Term Follow-Up	
For subjects who receive at least one CAB/RPV injection and permanently discontinue study treatment: Assessment Date > LTFU ART Start Date

- Date = start or assessment date
- [a] If participants have missing LTFU ART start date, only the lower bound will be considered in the derivation.

Study phase of discontinuation will be determined according to Table 9.

Table 9 Study Phases for Study Conclusion/IP Discontinuation

Study Phase	Definition

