13.6.2.1. Handling of Missing and Partial Dates

Element	Reporting Detail		
General	
 Partial dates will be displayed as captured in participant listing displays. Where necessary, display macros may impute dates as temporary variables for sorting data in listings only. In addition, partial dates may be imputed for ‘slotting’ data to study phases or for specific analysis purposes as outlined below. Imputed partial dates will not be used to derive study day, time to onset or duration (e.g., time to onset or duration of adverse events), or elapsed time variables (e.g., time since diagnosis). In addition, imputed dates are not used for deriving the last contact date in overall survival analysis dataset. 		
Adverse Events	
 Imputations in the adverse events dataset are used for slotting events to the appropriate study time periods and for sorting in data listings. Partial dates for AEs recorded in the CRF will be imputed using the following conventions: 
 
 Missing start day	 
 If study treatment start date is missing (i.e. participant did not start study treatment), then set start date = 1st of month. Else if study treatment start date is not missing: 
 If month and year of start date = month and year of study treatment start date, then 	
 
 	Missing start day	
 If study treatment start date is missing (i.e. participant did not start study treatment), then set start date = 1st of month. Else if study treatment start date is not missing: 
 If month and year of start date = month and year of study treatment start date, then
Missing start day	
 If study treatment start date is missing (i.e. participant did not start study treatment), then set start date = 1st of month. Else if study treatment start date is not missing: 
 If month and year of start date = month and year of study treatment start date, then 		

Element	Reporting Detail					

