Non-ART Medications (including Oral Bridging CAB + RPV)		
 • Completely missing start or end dates will remain missing, with no imputation applied. • Partial dates for any concomitant medications recorded in the CRF will be imputed using the following convention: 
  
 Missing start day	 
 • If study treatment start date is missing (i.e. participant did not start study treatment), then set start date = 1st of month. • Else if study treatment start date is not missing: 
 ○ If month and year of start date = month and year of study treatment start date, then 
 ▪ If stop date contains a full date and stop date is earlier than study treatment start date, then set start date= 1st of month. ▪ Else set start date = study treatment start date. ○ Else set start date = 1st of month. 	
 
 Missing start day and month	 
 • If study treatment start date is missing (i.e. participant did not start study treatment), then set start date = January 1. • Else if study treatment start date is not missing: 
 ○ If year of start date = year of study treatment start date, then 
 ▪ If stop date contains a full date and stop date is earlier than study treatment start date, then set start date = January 1. ▪ Else set start date = study treatment start date. • Else set start date = January 1. 	
  
 	Missing start day	
 • If study treatment start date is missing (i.e. participant did not start study treatment), then set start date = 1st of month. • Else if study treatment start date is not missing: 
 ○ If month and year of start date = month and year of study treatment start date, then 
 ▪ If stop date contains a full date and stop date is earlier than study treatment start date, then set start date= 1st of month. ▪ Else set start date = study treatment start date. ○ Else set start date = 1st of month. 	Missing start day and month	
 • If study treatment start date is missing (i.e. participant did not start study treatment), then set start date = January 1. • Else if study treatment start date is not missing: 
 ○ If year of start date = year of study treatment start date, then 
 ▪ If stop date contains a full date and stop date is earlier than study treatment start date, then set start date = January 1. ▪ Else set start date = study treatment start date. • Else set start date = January 1.

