ART Medications	
 Partial dates recorded in the eCRF will be imputed using the following convention: 
 If the partial date is a start date, a '01' will be used for the day and 'Jan' will be used for the month. If the partial date is a stop date, a '28/29/30/31' will be used for the day (dependent on the month and year) and 'Dec' will be used for the month. If medications recorded in the PRIOR ART form of the eCRF, then the earlier date of the imputed and the day prior to the maintenance phase treatment start date will be used, i.e. min (imputed stop date, Intervention phase treatment start date - 1). For medications with completely missing start date, they will be considered started prior to the Intervention phase treatment start date. For medications with completely missing stop date, they will be considered ongoing unless recorded in the PRIOR ART form of the eCRF. For ART booster medications, the start and stop dates are not recorded in the database (i.e. missing), the dates will be imputed to be the same as the dates of their parent medications. The recorded partial or missing date will be displayed in listings. 						

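### A partial start date for long-term follow-up ART is set to the 1st of the month (or January) with no floor, so on-treatment viral loads and AEs from the same month can be assigned to LTFU

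*SAP*

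**What the plan says.** SAP 13.6.2.1, ART Medications row: "If the partial date is a start date, a '01' will be used for the day and 'Jan' will be used for the month". The row's only cap is on stop dates from the prior-ART form, which may not run past the day before study treatment began. The introduction to the same section allows partial dates to be imputed for slotting "data to study phases or for specific analysis purposes as outlined below", with one restriction: "Imputed partial dates will not be used to derive study day, time to onset or duration".

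SAP 13.3.1 then uses the ART date as a phase boundary:

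- Entry to LTFU: "They are considered to enter the LTFU period if they have a post-treatment, non-bridging ART start date or LTFU visit entered in the CRF".
- Laboratory data, including HIV-1 RNA, belong to LTFU when "Assessment Date > LTFU ART Start Date" (Table 8).
- AEs belong to LTFU when "AE Start Date ≥ LTFU ART Start Date" (Table 7). The one exception is an AE leading to treatment withdrawal that starts exactly on the LTFU ART start date.
- A footnote to Tables 7 and 8 deals with a missing LTFU ART start date. It does not mention a partial one.

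Under SAP 13.3.2, treatment state is set only after the phase has been assigned, and everything in LTFU is post-treatment. Under SAP 13.5.3, the Snapshot takes the last HIV-1 RNA value in the window while the participant is on treatment in the Intervention Phase.

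**The concern.** An earliest-possible date is a sensible default for ART taken before the study. For ART started after study treatment, the same default can only place the phase boundary on or before its true position, never after it. The rule that counts data as on treatment up to 63 days after the last injection cannot rescue a misplaced record, because it is applied after phase assignment. A fully missing date is handled by the footnote, whereas a partial date, which carries more information, can misplace data.

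The exposed participants are those who stopped treatment, and their last viral load and last AEs matter most for the Snapshot, for virologic failure and for the discontinuation tables. Protocol 4.3.4 makes a visit close to the ART start plausible: HAART is due within about two months of the last injection, when the next dosing visit would also fall, or as soon as virologic failure is confirmed.

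**Working it through.** There is no figure in the plan to reproduce, so the SAP rules were applied to constructed records. The schedule follows the protocol's example (Dose 1 on 15 January). The year 2021, the oral start on 15 December 2020 and the HAART dates are assumptions.

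**Record A: Month 12 visit attended without Dose 7, HAART started that day.** The last injection is 15 October and the Month 12 visit with HIV-1 RNA is 15 December.
- On-treatment limit: 15 October + 63 days = 17 December, so the value is on treatment.
- Snapshot window: 15 December ± 42 days = 3 November to 26 January, so the value is in the window.
- True ART date 15 December: the value is Intervention and on treatment.
- Recorded as December only: imputed 1 December, and 15 December > 1 December, so the value becomes LTFU and post-treatment.
- Routine HIV-1 RNA is scheduled at Months 8 and 12 but not Month 10, so no other scheduled value falls in the window. Appendix 8 then classifies the participant by reason for stopping and last earlier viral load. A suppressed participant who stopped for a non-safety reason changes from <50 c/mL to no virologic data. In the other direction, a Month 12 value ≥50 after an earlier value <50 also becomes no virologic data, which hides a failure.

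**Record B: confirmation of virologic failure.** The last injection and the suspected failure are on 15 August, the confirmatory sample on 5 September, and HAART starts on 20 September.
- On-treatment limit: 15 August + 63 days = 17 October.
- Recorded as September only: imputed 1 September. The 5 September viral load and any AE starting from 1 September (apart from an AE leading to withdrawal that starts on that very day) move to LTFU, where Protocol 7.1.8 says the definition of confirmed virologic failure does not apply.

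**Record C: HAART two months after the last visit.** The last injection is 15 August, HAART starts on 15 October, and there is no October visit.
- Recorded as October only: imputed 1 October. No visit moves.

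**Month also missing.** The imputed date is 1 January 2021, before Dose 1. If that date is used, all five visits tested in record A (15 January to 15 December), both in record B and both tested in record C (15 June and 15 August) fall in LTFU.

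**How often a missing day would move the last visit.** Assume a 30-day month, visit day d uniform on 1 to 28 and a uniform gap from last visit to HAART. The visit moves if HAART falls in the same month and d > 1.
- Gap 0 to 14 days: d = 2 to 16 gives 15 × 15 = 225; d = 17 to 28 gives 14 + 13 + … + 3 = 102. The share is 327 / (28 × 15) = 78%.
- Gap 0 to 67 days (last visit is the last injection, HAART at any time up to 2 months + 7 days): 29 + 28 + … + 3 = 432. The share is 432 / (28 × 68) = 23%.
- Gap 53 to 67 days (2 months ± 7 days): 0%.

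These shares are conditional on the day being missing. The documents do not give that frequency.

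**Size per participant:** 1 / 450 = 0.22 percentage points.

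**The case against.** The strongest objection is that the trigger should be rare. The choice and timing of HAART are to be discussed with the Medical Monitor before it starts, HAART dispensation is a scheduled activity, dates of administration are a minimum recording requirement, and the database is cleaned before the Month 12 analysis. This stands: the frequency is unknown and may be zero. It bears on the size of the problem and leaves the rule itself incorrect.

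A reader might draw several stronger conclusions that the documents do not support:

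- *That a missing month certainly sends a year of data to LTFU.* Entry through ART requires a start date that is post-treatment. Read as a date filter, that term might reject 1 January. The SAP does not define it so, and the outcome is ambiguous. A filter would still not protect visits between the last dose and the true ART start, as in records A and B.
- *That Month 12 results of Extension participants are affected.* Phases are assigned in sequence from the top of each table, so their data before Month 14 stay in the Intervention Phase. Only their Extension data are exposed.
- *That LTFU study day and exposure are distorted.* Their formulas contain the LTFU ART start date, but the SAP bars imputed dates from study day and duration.
- *That the AE and non-ART rules contain the protection missing here.* Their floor ("Else set start date = study treatment start date") applies only in the month or year in which study treatment began. It would not help a date near the end of treatment.
- *That moved AEs disappear.* They would be reported in the LTFU tables instead, and AEs leading to discontinuation have their own LTFU table and a listing.

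The present rule is also sometimes right: if HAART really began before the visit, that viral load should not count for the study regimen.

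**Conclusion.** The concern holds in a limited form. SAP 13.6.2.1 can misassign truly on-treatment data to LTFU for participants who received at least one injection, permanently discontinued, and have a partial LTFU ART start date. With only the day missing, the visit or AE must fall in the same calendar month as the ART start. With the month missing, the reach back to January depends on how an undefined term is read.

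Each affected participant changes a Month 12 proportion by about 0.2 percentage points of 450. No total can be given, because the documents do not report how many such dates to expect and the share of last visits moved runs from 0% to 78% across the assumed HAART gaps. The clinical efficacy endpoints concerned are secondary and descriptive. This is a minor correction, worth making because it is cheap and the error falls only on participants who stopped.

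**What to change.** In SAP 13.6.2.1, keep the 01/January rule for prior ART. For ART recorded as started after study treatment and not as bridging, impute a partial start date as the latest of:

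- the 1st of the recorded month (or 1 January of the recorded year);
- the day after the last study dose;
- the day after the last Intervention or Extension visit as labelled in the eCRF.

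Cap the result at the end of the recorded month or year and at any recorded ART stop date. The visit must be the recorded one: a derived on-treatment visit would be circular, because treatment state depends on phase and phase depends on this date. Using the day after the visit keeps an AE that starts on the visit day in the Intervention Phase. State that unscheduled viral-load retests before the first LTFU visit count as visits; otherwise a confirmatory sample such as that in record B stays unprotected. The cap prevents a start recorded as February from being moved to a visit on 14 March.

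The downside is that a viral load taken just after an undated HAART start could be counted as on treatment. List the participants with an imputed LTFU ART start date so that this can be seen. The cost is a short amendment to one table row, the matching change in the date-imputation program, and one listing.

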13.6.2.2. Handling of Missing Data for Statistical Analysis

Element	Reporting Detail
Snapshot	
 In the Snapshot dataset, subjects without HIV – 1 RNA data in the assessment window for the visit of interest (due to missing data or discontinuation of IP prior to the visit window) do not belong to 'HIV-1 < 50 c/mL (or 200 c/mL)'. The nature of this missing data will be further classified in Snapshot summaries as either 'HIV-1 RNA ≥ 50' or 'No Virologic Data at Week X'; See Appendix 8: Snapshot Algorithm Details Note: The primary snapshot analysis will not impute any missing data due to Covid-19 and will consider Covid-19 related missing data in accordance with all other missing data.

13.7. Appendix 7: Values of Potential Clinical Importance

Values of clinical importance will be summarized for hepatobiliary abnormalities. Abnormal laboratory value grades will be assigned as specified by protocol Section 10.2. Liver chemistry stopping criteria can be found in the protocol Section 10.3.1.

13.7.1. Hepatobiliary Abnormality Criteria

Element	Reporting Detail
General	
 To include ALT, ALP, Bilirubin, & INR parameters
ALT \geq 3xULN and BIL \geq 2xULN	
 If direct bilirubin is available (on the same date as Total Bilirubin), then direct bilirubin as a portion of total bilirubin must be \geq35% when total bilirubin is \geq2xULN, in order to satisfy the criteria. Bilirubin value is on or up to 28 days after ALT value.
ALT \geq 3xULN and INR $>$ 1.5	
 INR value is on or up to 28 days after ALT value.
ALT \geq 3xULN and BIL \geq 2xULN and ALP 2 (<1%) $<$ 2xULN	
 If direct bilirubin is available (on the same date as Total Bilirubin), then direct bilirubin as a portion of total bilirubin must be \geq35% when total bilirubin is \geq2xULN, in order to satisfy the criteria. Bilirubin value is on or up to 28 days after ALT value. The ALP value must occur on or up to 28 days after the ALT value.
Hepatocellular injury	
 Hepatocellular injury is defined as $((\text{ALT}/\text{ALT ULN})/(\text{ALP}/\text{ALP ULN})) \geq 5$ and ALT \geq3xULN. ALT and ALP values must occur on the same day.
Hepatocellular injury and BIL \geq 2xULN	
 Hepatocellular injury is defined as $((\text{ALT}/\text{ALT ULN})/(\text{ALP}/\text{ALP ULN})) \geq 5$ and ALT \geq3xULN. ALT and ALP values must occur on the same day. If direct bilirubin is available (on the same date as Total Bilirubin), then direct bilirubin as a portion of total bilirubin must be \geq35% when total bilirubin is \geq2xULN, in order to satisfy the criteria. Bilirubin value is on or up to 28 days after ALT value.
BIL \geq 2xULN	
 If direct bilirubin is available (on the same date as Total Bilirubin), then direct bilirubin as a portion of total bilirubin must be \geq35% when total bilirubin is \geq2xULN, in order to satisfy the criteria.
AST $>$ 3xULN and ALP $<$ 2xULN and BIL \geq 2xULN	
 ALP and BIL values must occur on or up to 28 days after AST value. If direct bilirubin is available (on the same date as Total Bilirubin), then direct bilirubin as a portion of total bilirubin must be \geq35% when total bilirubin is \geq2xULN, in order to satisfy the criteria.
ALT $>$ X ULN and AST $>$ X ULN	
 AST and ALT values must occur on the same day

13.8. Appendix 8: Snapshot Algorithm Details

Detailed Algorithm Steps

 • Consider an analysis visit window for Month X as defined in Table 2. • The HIV-1 RNA threshold of 50 will be analysed in this study • The COVID-19 pandemic presents significant logistical challenges for many clinical sites around the world, with variable restrictions being placed on site resources and operations, and on an individual participants ability to attend clinic visits. The snapshot algorithm is modified to allow for the presentation of full scope of COVID-19 relatedness. The analysis window for 'Month 12' and HIV-1 RNA threshold of '50 c/mL' are used for the purpose of illustration. A participant's Snapshot response and reason at Month 12 are categorized as below. 
 ○ HIV-1 RNA < 50 c/mL ○ HIV-1 RNA ≥ 50 c/mL 
 Data in window not below 50 
 Non-COVID-19 related 
 Discontinued for lack of efficacy Discontinued for other reason while not below 50 COVID-19 related 
 Discontinued for lack of efficacy Discontinued for other reason while not below 50 ○ No Virologic Data at Month 12 Window 
 Non-COVID-19 related 
 Discontinued study due to AE or death Discontinued study for other reasons On study but missing data in window COVID-19 related 
 Discontinued study due to AE or death Discontinued study for other reasons On study but missing data in window Change in background therapy* 
* Note: Use of CAB + RPV oral bridging and SOC oral bridging medication, where the latter is due to unavailability of CAB/RPV IM injections or oral CAB+RPV during the pandemic, will not be considered a "Change in background therapy" in the Snapshot algorithm. All other permanent changes in ART are not permitted in this protocol.

Detailed steps
 
 • Please note that the following scenarios will NOT be penalized in the Snapshot algorithm Oral bridging (CAB+RPV or SOC, where SOC oral bridging medication is permitted during COVID-19 pandemic due to the unavailability of the CAB/RPV IM injections and oral CAB+RPV)

Detailed Algorithm Steps		
Condition ('Month 12' indicates Month 12 window)	Response	Reasons
1. If non-permitted change in background therapy prior to Month 12	HIV-1 RNA \geq 50	Change in background therapy
2. If non-permitted change in background therapy during Month 12		

 Last on-treatment VL during Month 12 prior to/on the date of change \geq 50 c/mL 	HIV-1 RNA \geq 50	Data in window not below 50

 Last on-treatment VL during Month 12 prior to/on the date of change $<$ 50 c/mL 	HIV-1 RNA $<$ 50	

 No VL during Month 12 prior to/on the date of change 	HIV-1 RNA \geq 50	Change in background therapy
3. If none of the above conditions met		
3.1. On-treatment VL available during Month 12		

 Last on-treatment VL during Month 12 \geq 50 c/mL 	HIV-1 RNA \geq 50	Data in window not below 50

 Last on-treatment VL during Month 12 $<$ 50 c/mL 	HIV-1 RNA $<$ 50	
3.2. No on-treatment VL during Month 12		
3.2.1. If participants are still on study, i.e. a participant has not permanently discontinued the study treatment yet, or if a participant permanently discontinued the study treatment and the upper bound of analysis snapshot window is prior to the following date: 
 Min[max(Date of last injection + 35, Date of Last Dose of Oral Study Treatment (CAB+RPV, SOC Bridging) + 1), LTFU ART Start Date] 		
3.2.1.1. If no on-treatment VL during Month 12 is not due to COVID-19	No virologic data at Month 12 Window	On study but missing data in window (Non-COVID-19 related)
3.2.1.2. If no on-treatment VL during Month 12 is due to COVID-19	No virologic data at Month 12 Window	On study but missing data in window (COVID-19 related)
